#### 10.4 Expedited Reporting Requirements for IND Agents

##### 10.41 Expedited Reporting Requirements for Adverse Events that Occur on Studies under an IND/IDE within 30 Days of the Last Administration of the Investigational Agent/Intervention

###### FDA REPORTING REQUIREMENTS FOR SERIOUS ADVERSE EVENTS (21 CFR Part 312)

**NOTE:** Investigators **MUST** immediately report to the sponsor **ANY** Serious Adverse Events, whether or not they are considered related to the investigational agent(s)/intervention (21 CFR 312.64)

An adverse event is considered serious if it results in **ANY** of the following outcomes:

- 1) Death
- 2) A life-threatening adverse event
- 3) An adverse event that results in inpatient hospitalization or prolongation of existing hospitalization for ≥ 24 hours
- 4) A persistent or significant incapacity or substantial disruption of the ability to conduct normal life functions
- 5) A congenital anomaly/birth defect.
- 6) Important Medical Events (IME) that may not result in death, be life threatening, or require hospitalization may be considered serious when, based upon medical judgment, they may jeopardize the patient or subject and may require medical or surgical intervention to prevent one of the outcomes listed in this definition. (FDA, 21 CFR 312.32; ICH E2A and ICH E6).

**ALL SERIOUS** adverse events that meet the above criteria **MUST** be immediately reported to the sponsor within the timeframes detailed in the table below.

Hospitalization	Grade 1 and Grade 2 Timeframes	Grade 3-5 Timeframes
Resulting in Hospitalization ≥24 hrs	7 Calendar Days	24-Hour 3 Calendar Days
Not resulting in Hospitalization ≥24 hrs	Not required	

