## 10.0 Adverse Event (AE) Monitoring and Reporting

The site principal investigator is responsible for reporting any/all serious adverse events to the sponsor as described within the protocol, regardless of attribution to study agent or treatment procedure.

The sponsor/sponsor-investigator is responsible for notifying FDA and all participating investigators in a written safety report of any of the following:

- Any suspected adverse reaction that is both serious and unexpected.
- Any findings from laboratory animal or *in vitro* testing that suggest a significant risk for human subjects, including reports of mutagenicity, teratogenicity, or carcinogenicity.
- Any findings from epidemiological studies, pooled analysis of multiple studies, or clinical studies, whether or not conducted under an IND and whether or not conducted by the sponsor, that suggest a significant risk in humans exposed to the drug
- Any clinically important increase in the rate of a serious suspected adverse reaction over the rate stated in the protocol or Investigator's Brochure (IB).

Summary of SAE Reporting for this study  
(please read entire section for specific instructions):

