#### 10.43 Reporting of re-occurring SAEs

ALL SERIOUS adverse events that meet the criteria outlined in table 10.41 MUST be immediately reported to the sponsor within the timeframes detailed in the corresponding table. This reporting includes, but is not limited to SAEs that re-occur again after resolution.

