#### 10.54 Second Malignancy

A second malignancy is one unrelated to the treatment of a prior malignancy (and is

NOT a metastasis from the initial malignancy). Second malignancies require ONLY routine reporting unless otherwise specified.

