#### **Immediate Reporting of Adverse Events to Merck**

##### **Serious Adverse Events**

A serious adverse event is any adverse event occurring at any dose or during any use of Merck’s product that:

- Results in death;
- Is life threatening;
- Results in persistent or significant disability/incapacity;
- Results in or prolongs an existing inpatient hospitalization;

- Is a congenital anomaly/birth defect;
- Is a new cancer (that is not a condition of the study);
- Is associated with an overdose;
- Is another important medical event

Any serious adverse event, or follow up to a serious adverse event, including death due to any cause other than progression of the cancer under study that occurs to any subject from the time the consent is signed through 90 days following cessation of treatment, or the initiation of new anti-cancer therapy, whichever is earlier, whether or not related to Merck product, must be reported within 24 hours to the Sponsor and within 2 working days to Merck Global Safety.

Non-serious Events of Clinical Interest will be forwarded to Merck Global Safety and will be handled in the same manner as SAEs.

Additionally, any serious adverse event, considered by an investigator who is a qualified physician to be related to Merck product that is brought to the attention of the investigator at any time outside of the time period specified in the previous paragraph also must be reported immediately to the Sponsor and to Merck.

**SAE reports and any other relevant safety information are to be forwarded to the Merck Global Safety facsimile number: [REDACTED]**

A copy of all 15 Day Reports and Annual Progress Reports is submitted as required by FDA, or other local regulators. Investigators will cross reference this submission according to local regulations to the Merck Investigational Compound Number (IND, CSA, etc.) at the time of submission. Additionally investigators will submit a copy of these reports to Merck & Co., [REDACTED] at the time of submission to FDA.

All subjects with serious adverse events must be followed up for outcome.

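### The 10.41 table requires no expedited report for Grade 1-2 events without a 24-hour hospital stay, although 10.41's own text and 10.81 require serious events of that kind to reach the sponsor

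*Combined protocol and SAP*

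**What the plan says.** Section 10.41 opens with a note that investigators must immediately report any serious adverse event to the sponsor, related or not. It then lists six criteria for seriousness: death; life-threatening event; hospitalization or its prolongation, with a 24-hour threshold; incapacity; congenital anomaly; and important medical event. The sentence above the table says that all serious "adverse events that meet the above criteria MUST be immediately reported to the sponsor within the timeframes detailed in the table below".

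The table has two rows (with or without a hospital stay of at least 24 hours) and two grade bands (1-2 and 3-5). For a Grade 1-2 event with such a stay it sets 7 calendar days. For Grade 3-5 it sets 24 hours, with the complete report 3 calendar days later. In the row "Not resulting in Hospitalization ≥24 hrs", the Grade 1-2 entry is that reporting is not required.

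Section 10.43 says of recurring events: "ALL SERIOUS adverse events that meet the criteria outlined in table 10.41 MUST be immediately reported to the sponsor", again within the timeframes of that table. Section 10.81 says that any serious event from consent to 90 days after treatment, or to the start of new anti-cancer therapy if earlier, "whether or not related to Merck product, must be reported within 24 hours to the Sponsor". It excepts death from progression of the cancer under study, and sets no limit by grade or length of stay.

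**The concern.** Seriousness and grade are separate ideas, and the note at the end of 10.1 says that severe is not the same as serious. The 10.41 table nevertheless sorts serious events by grade and hospital stay, and one resulting cell removes events that the sentence above it makes mandatory.

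At stake is what the sponsor sees in time. Section 10.0 makes the sponsor responsible for telling FDA and the participating investigators of "Any suspected adverse reaction that is both serious and unexpected", and it can do this only for events that sites send. Immune-related events managed without admission are the kind whose seriousness may rest on the important-medical-event criterion alone. Completeness matters here: 15.27 records more serious side effects and deaths when pembrolizumab was added to pomalidomide or lenalidomide with dexamethasone in myeloma.

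**Working it through.** No arithmetic applies. The check sets the 10.41 criteria against the 10.41 table, then follows an event in the disputed cell through the other reporting routes.

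**Step 1. Which 10.41 criteria can fall in the cell for Grade 1-2 without a 24-hour stay?**

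- Criterion 1 (death): no. It is Grade 5.
- Criterion 2 (life-threatening): not in practice. Such events are graded above 2.
- Criterion 3 (hospitalization): no, if the 24-hour threshold is read as applying to the whole criterion. The event then falls in the other row.
- Criterion 4 (incapacity): yes. It sets neither a stay nor a grade.
- Criterion 5 (congenital anomaly): yes by its wording, but 10.55 already requires a separate expedited report for a birth defect.
- Criterion 6 (important medical event): yes. It expressly covers events that do not lead to hospitalization.

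Three criteria can fall in the cell. Two of them, 4 and 6, have no other dedicated route.

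**Step 2. What does each section ask for such an event?**

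- 10.41, note and sentence above the table: immediate report to the sponsor.
- 10.41, table: no report required.
- 10.43: report, but with timeframes taken from the disputed table. It adds no independent support.
- 10.81: to the sponsor within 24 hours, within its window.
- 10.82: all serious events go to the second drug supplier, so the sponsor-investigator must receive them.
- 10.0: all serious events go to the sponsor, but as the protocol describes, which leads back to 10.41.

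**Step 3. Does routine reporting catch what the table waives?** Only in part. Section 10.62 adds related Grade 2 events, Grade 3-4 events and deaths to the terms listed in 10.61. A Grade 1 event, or an unrelated Grade 2 event, that is not a 10.61 term is not among the events to submit. Section 10.81 does have all adverse events recorded on case report forms or worksheets up to 30 days after treatment.

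**Step 4. An example.** The table in 8.2 acts on myocarditis from Grade 1. Suppose a Grade 1 case is judged an important medical event and managed without admission. The 10.41 table requires no report. Myocarditis is not in 10.61, Grade 1 is outside 10.62, and neither event of clinical interest named in 10.81 (symptom-free overdose, a liver-test pattern) covers it. The serious-event rule in 10.81 requires it within 24 hours. A related Grade 2 pneumonitis differs: 10.621 brings it in by routine reporting, though not as an expedited report.

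**Step 5. Events after 30 days.** Footnote 1 to 10.41 covers serious events with at least possible attribution more than 30 days after the last administration. It expedites Grade 3-5 events and, below that, only Grade 2 events with hospitalization or its prolongation. A related serious Grade 1 event, or a related serious Grade 2 event without hospitalization, is again left out, while the 10.81 window runs to 90 days or new therapy.

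In the extracted text the Grade 3-5 entry of the lower row is blank. I read it as one entry spanning both rows; the point does not depend on this.

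**The case against.** The strongest reply is that the table governs expedited reporting. A reader might infer that a serious event could stay wholly unreported to the sponsor; the documents do not support that as a general statement. The note in 10.41, 10.0, 10.81 and 10.82 all state the wider duty, 10.82 has sub-investigators report all serious events to the sponsor-investigator in a multisite setting, and 10.81 has every adverse event recorded. A site would have to follow the table and overlook the rest. This stands, and it limits the point to an instruction that contradicts itself and to the expedited report.

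A reader might also infer that birth defects, overdoses and new cancers fall through. They have routes: 10.55 for birth defects, and the overdose rule in 10.81, which requires notice to the sponsor within 24 hours. For new cancers, 10.54 reads "Second malignancies require ONLY routine reporting unless otherwise specified", and both 10.81 and 10.82 do specify otherwise. Section 10.54 is therefore not in conflict.

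The two lists of serious events do differ. Section 10.81 counts any inpatient hospitalization, a new cancer and an overdose-associated event. But 10.81 is a supplier-specific layer on the IND rule, and a site can satisfy both by applying both. That calls for a cross-reference; it does not show an error.

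Finally, some serious events are exempt by design. The 10.32 list of expected events and its list of hospitalizations that are not serious events are deliberate. Neither explains a waiver for every Grade 1-2 event without a 24-hour stay.

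**Conclusion.** The contradiction is real and sits inside 10.41, with 10.81 as independent confirmation. It affects one of four table cells and, in practice, events serious through incapacity or important-medical-event status. A site that follows the table would send no expedited report. For a Grade 1 or unrelated Grade 2 event outside the 10.61 list, 10.62 would not ask for one either.

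The consequence is for safety reporting. A reader might infer that the toxicity results under goal 2.23 would be distorted. The plan does not support this: 16.325 tabulates maximum grade by type of event, no serious-event count is planned, the dose-limiting toxicities in 16.4 start at Grade 3, and the stopping rules in 16.52 use Grade 4 or higher. The primary endpoint is not touched.

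The documents give no rate for low-grade serious events managed without a 24-hour stay, so a patient count would only restate whatever rate was assumed. The conclusion rests on the wording alone and on reading the 24-hour threshold as applying to all of criterion 3. It should be corrected.

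**What to change.** - In the 10.41 table, limit the not-required entry to non-serious events. Give serious Grade 1-2 events without a 24-hour stay a sponsor timeframe consistent with 10.81.
- State that the 10.32 exceptions, and its list of hospitalizations that are not serious events, continue to apply.
- Reconcile footnote 1 to 10.41 in the same way, since it repeats the hospitalization limit for Grade 2 events after 30 days.
- Add a cross-reference in 10.41 to the broader serious-event list in 10.81 (any inpatient hospitalization, new cancer, overdose-associated event).

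The cost is a wording change to the 10.41 table, its footnote and one cross-reference. The downside is a few more expedited reports, which 10.81 already requires within its window. Section 10.54 needs no change, and neither sample size nor analysis is affected.

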###### Expedited AE reporting timelines are defined as:

- "24-Hour; 3 Calendar Days" - The AE must initially be reported within 24 hours of learning of the AE, followed by a complete expedited report within 3 calendar days of the initial 24-hour report.
- "7 Calendar Days" - A complete expedited report on the AE must be submitted within 7 calendar days of learning of the AE.

Serious adverse events that occur more than 30 days after the last administration of investigational agent/intervention and have an attribution of possible, probable, or definite require reporting as follows:

**Expedited 24-hour notification followed by complete report within 3 calendar days for:**

- All Grade 3, 4, and Grade 5 AEs

**Expedited 7 calendar day reports for:**

- Grade 2 AEs resulting in hospitalization or prolongation of hospitalization

 For studies using PET or SPECT IND agents, the AE reporting period is limited to 10 radioactive half-lives, rounded UP to the nearest whole day, after the agent/intervention was last administered. Footnote "1" above applies after this reporting period.

Effective Date: May 5, 2011

NOTE: Refer to Section 10.32 for exceptions to Expedited Reporting

#### 10.42 General reporting instructions

The Mayo IND Coordinator will assist the sponsor-investigator in the processing of expedited adverse events and forwarding of suspected unexpected serious adverse reactions (SUSARs) to the FDA and IRB.

Use Mayo Expedited Event Report form

[REDACTED] investigational agents or commercial/investigational agents on the same arm.

#### 10.43 Reporting of re-occurring SAEs

ALL SERIOUS adverse events that meet the criteria outlined in table 10.41 MUST be immediately reported to the sponsor within the timeframes detailed in the corresponding table. This reporting includes, but is not limited to SAEs that re-occur again after resolution.

#### 10.5 Other Required Reporting

##### 10.51 Unanticipated Problems Involving Risks to Subjects or Others (UPIRTSOS)

Unanticipated Problems Involving Risks to Subjects or Others (UPIRTSOS) in general, include any incident, experience, or outcome that meets **all** of the following criteria:

1. Unexpected (in terms of nature, severity, or frequency) given (a) the research procedures that are described in the protocol-related documents, such as the IRB-approved research protocol and informed consent document; and (b) the characteristics of the subject population being studied;
2. Related or possibly related to participation in the research (in this guidance document, possibly related means there is a reasonable possibility that the incident, experience, or outcome may have been caused by the procedures involved in the research); and
3. Suggests that the research places subjects or others at a greater risk of harm (including physical, psychological, economic, or social harm) than was previously known or recognized.

Some unanticipated problems involve social or economic harm instead of the physical or psychological harm associated with adverse events. In other cases, unanticipated problems place subjects or others at increased *risk* of harm, but no harm occurs.

Note: If there is no language in the protocol indicating that pregnancy is not considered an adverse experience for this trial, and if the consent form does not indicate that subjects should not get pregnant/impregnate others, then any pregnancy in a subject/patient or a male patient's partner (spontaneously reported) which occurs during the study or within 120 days of completing the study should be reported as a UPIRTSO.

##### **Mayo Clinic Cancer Center (MCCC) Institutions:**

If the event meets the criteria for IRB submission as a Reportable Event/UPIRTSO, provide the Reportable Event Report Form

[REDACTED] The Mayo Clinic Compliance Unit will review and process the submission to the Mayo Clinic IRB and work with the IND Coordinator for submission to FDA.

#### 10.52 Death

**Note: A death on study requires both routine and expedited reporting regardless of causality, unless as noted below. Attribution to treatment or other cause must be provided.**

Any death occurring within 30 days of the last dose, regardless of attribution to an agent/intervention under an IND/IDE requires expedited reporting within 24-hours.

Any death occurring greater than 30 days with an attribution of possible, probable, or definite to an agent/intervention under an IND/IDE requires expedited reporting within 24-hours.

##### **Reportable categories of Death**

- Death attributable to a CTCAE term.
- Death Neonatal: A disorder characterized by cessation of life during the first 28 days of life.
- Death NOS: A cessation of life that cannot be attributed to a CTCAE term associated with Grade 5.
- Sudden death NOS: A sudden (defined as instant or within one hour of the onset of symptoms) or an unobserved cessation of life that cannot be attributed to a CTCAE term associated with Grade 5.
- Death due to progressive disease should be reported as **Grade 5 “Neoplasms benign, malignant and unspecified (including cysts and polyps) – Other (Progressive Disease)”** under the system organ class (SOC) of the same name. Evidence that the death was a manifestation of underlying disease (e.g., radiological changes suggesting tumor growth or progression; clinical deterioration associated with a disease process) should be submitted.

#### 10.53 Secondary Malignancy

- A **secondary malignancy** is a cancer caused by treatment for a previous malignancy (e.g., treatment with investigational agent/intervention, radiation or chemotherapy). A secondary malignancy is not considered a metastasis of the initial neoplasm.
- All secondary malignancies that occur following treatment with an agent under an IND/IDE will be reported. Three options are available to describe the event:
  - Leukemia secondary to oncology chemotherapy (e.g., Acute Myelocytic Leukemia [AML])
  - Myelodysplastic syndrome (MDS)
  - Treatment-related secondary malignancy
- Any malignancy possibly related to cancer treatment (including AML/MDS) should also be reported via the routine reporting mechanisms outlined in each protocol.

#### 10.54 Second Malignancy

A second malignancy is one unrelated to the treatment of a prior malignancy (and is

NOT a metastasis from the initial malignancy). Second malignancies require ONLY routine reporting unless otherwise specified.

10.55 Pregnancy, Fetal Death, and Death Neonatal

If a female subject (or female partner of a male subject) taking investigational product becomes pregnant, the subject taking should notify the Investigator, and the pregnant female should be advised to call her healthcare provider immediately. The patient should have appropriate follow-up as deemed necessary by her physician. If the baby is born with a birth defect or anomaly, a second expedited report is required.

Prior to obtaining private information about a pregnant woman and her infant, the investigator must obtain consent from the pregnant woman and the newborn infant's parent or legal guardian before any data collection can occur. A consent form will need to be submitted to the IRB for these subjects if a pregnancy occurs. If informed consent is not obtained, no information may be collected.

In cases of fetal death, miscarriage or abortion, the mother is the patient. In cases where the child/fetus experiences a serious adverse event other than fetal death, the child/fetus is the patient.

NOTE: When submitting Mayo Expedited Adverse Event Report reports for "Pregnancy", "Pregnancy loss", or "Neonatal loss", the potential risk of exposure of the fetus to the investigational agent(s) or chemotherapy agent(s) should be documented in the "Description of Event" section. Include any available medical documentation. Include this form:

10.551 Pregnancy

Pregnancy should be reported in an expedited manner as **Grade 3 "Pregnancy, puerperium and perinatal conditions - Other (pregnancy)"** under the Pregnancy, puerperium and perinatal conditions SOC. Pregnancy should be followed until the outcome is known.

10.552 Fetal Death

Fetal death is defined in CTCAE as "A disorder characterized by death in utero; failure of the product of conception to show evidence of respiration, heartbeat, or definite movement of a voluntary muscle after expulsion from the uterus, without possibility of resuscitation."

Any fetal death should be reported expeditiously, as **Grade 4 "Pregnancy, puerperium and perinatal conditions - Other (pregnancy loss)"** under the Pregnancy, puerperium and perinatal conditions SOC.

10.553 Death Neonatal

Neonatal death, defined in CTCAE as "A disorder characterized by cessation of life occurring during the first 28 days of life" that is felt by the investigator to be at least possibly due to the investigational agent/intervention, should be reported expeditiously.

A neonatal death should be reported expeditiously as **Grade 4 "General disorders and administration - Other (neonatal loss)"** under the General disorders and administration SOC.

## 10.6 Required Routine Reporting

### 10.61 Baseline and Adverse Events Evaluations

Pretreatment symptoms/conditions to be graded at baseline and adverse events to be graded at each evaluation.

Grading is per CTCAE v4.0 **unless** alternate grading is indicated in the table below:

CTCAE SYSTEM/ORGAN/CLASS	Adverse event/Symptoms	Baseline	Each evaluation
Blood and lymphatic system disorders	Febrile neutropenia	X	X
Gastrointestinal Disorders	Baseline # of stools	X	
	Constipation		X
	Diarrhea		X
	Nausea	X	X
	Vomiting	X	X
General disorders and administration site conditions	Fatigue	X	X
Infections and infestations	Sepsis	X	X
Investigations	Creatinine increased	X	X
	Neutrophil count decreased	X	X
	Platelet count decreased	X	X
Skin and subcutaneous tissue disorders	Rash, maculo-papular	X	X

